## 4.2. Schedule of Events

Tests and assessment	T0 (Enrollment)	T1 (12 weeks) ± 1 week	T2 (24 weeks) ± 1 week	ET Early termination
Inclusion/Exclusion criteria	X			
Informed consent	X			
Social-demographics (e.g., age, gender)	X			
Medical history (e.g., disease duration, previous disease history and treatments)	X			
On-treatment medical information (e.g., concomitant therapies, comorbidities)	X	X	X	X
Pregnancy hCG test	X			
Clinical and neurological evaluation (including recording of relapses and EDSS)	X	X	X	X
Drug Supply	X	X		
Assessment of patients' satisfaction (TSQM-9)	X	X	X	X
Assessment of patients' adherence	X	X	X	X
Assessment of patients' injection-system satisfaction (Adapted MSTCQ)	X	X	X	X
Assessment of patients' HRQoL (MusiqoL)	X	X	X	X
Assessment of patients' fatigue (FSS)	X	X	X	X
Routine Laboratory tests	X	X	X	X
Adverse events, pregnancy exposure, episodes of overdose		X	X	X
Drug Accountability 		X	X	X

1. If a dose is missed, it should be administered as soon as possible, within 7 days.

CONFIDENTIAL

The information contained herein may not be used, disclosed, or published without the written consent of Biogen Italia

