#### **16.3.4. Secondary Endpoints Analysis**

All the other endpoints will be analysed according to the same technique. Correlations between variables will be assessed by a Spearman rank correlation coefficient.

To evaluate the relationship between patients' satisfaction and social-demographic factors (age, sex, employment working, level of education, etc.) and clinical characteristics (ARR, disability, etc.) generalized linear mixed models for repeated measurements will be performed.

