In addition, routine clinical assessments will be performed in order to check the safety of the Peg-IFN ongoing treatment.

Laboratory Safety Assessments

At the Investigator's discretion, the following routine laboratory tests can be carried out, in order to monitor the safety profile of the ongoing treatment based on Peg-IFN:

- Hematology: RBC- WBC –Haemoglobin- Haematocrit- MCV- MCH – MCHC - Platelets Count – Lymphocytes- Monocytes – Neutrophils – Eosinophils – Basophils
- Blood chemistry: creatinine, blood urea nitrogen (BUN), alkaline phosphatase, ALT, AST, gamma-glutamyl-transferase (GGT).

A pregnancy hCG test (blood sample) will be performed at the baseline visit (T0) to exclude pregnancy, if applicable (it is not required if the subject is post-menopausal or surgically sterilized).

9. Missing data

For missing data in TSQM-9, MSTCQ and MusiQoI see paragraph Variable of analysis.

For the other variables no imputation technique will be apply.

10. Statistical analysis

The primary and secondary endpoints will be evaluated using a repeated measures ANOVA. The repeated measures ANOVA is used to compare group means on a dependent variable across repeated measurements of time. This statistical method is used for making simultaneous comparisons between two or more means of two or more related, not independent, groups.

However, in addition, it could be useful to apply a general linear mixed model that models for group means as fixed effects while simultaneously modeling for individual subject variables as random effects (12). This kind of model is a subject-specific model and is a choice for analysing longitudinal data. Unlike the repeated measures ANOVA, which requires a complete balanced array of data, the mixed model can accommodate a dataset with a large portion missing. Although the repeated measures ANOVA requires a fixed time schedule among all individual units, the mixed model can accommodate flexible time schedules. Furthermore, rather than treating time as a categorical variable, as in the repeated measures ANOVA, the mixed model is capable of treating time as either a continuous variable or a categorical variable or both.

Spearman's correlation coefficient measures the strength of association between two ranked variables.

Differences will be considered statistically significant if the p-value will be less or equal to a type I error =0.05 (two-sided test).

11. Efficacy data

a. Primary Endpoint Analysis

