The primary endpoint is to evaluate the changes from baseline in the score of convenience satisfaction domain of TSQM-9 at 12 weeks. (*Stata instruction: anova var1 time, repeated(time)*)

b. Secondary Endpoints Analysis

- Changes from baseline in the score of all domains of TSQM-9 at 24 weeks;
- Changes from baseline in patient adherence to study treatment survey at 12 and 24 weeks;
- Changes from baseline in the score of FSS (Fatigue Status Scale) at 12 and 24 weeks;
- Changes from baseline in the score of Adapted Sclerosis Treatment Concerns Questionnaire (MSTCQ) at 12 and 24 weeks;
- Changes from baseline in the score of Multiple Sclerosis International Quality of Life questionnaire (MusiQoL) at 12 and 24 weeks;
- Changes from baseline in clinical measures (ARR, percentage of relapse-free patients), measures at 24 weeks.

All the above primary and secondary endpoints will be analysed by a repeated measures analysis of variance adjusted for baseline factors (age, sex, disease duration, previous treatment duration, EDSS) (*Stata instruction: anova var1 var2 time, repeated(time)*).

Correlations between variables will be assessed by a Spearman rank correlation coefficient (*Stata instruction: spearman var1 var2*).

[figure not shown]
To evaluate the relationship between patients' satisfaction and social-demographic factors (age, sex, employment working, level of education, etc.) and clinical characteristics (ARR, disability, etc.) generalized linear mixed models for repeated measurements will be performed (*Stata instruction: mixed var1 var2 || patient:*).

12. Safety Data

a. Adverse events

All events will be coded using the Medical Dictionary for Regulatory Activities (MedDRA). Type and incidence of all AEs will be tabulated. Severity and drug relatedness of all reported AEs will be tabulated.

b. Clinical Laboratory Tests

	Statistical Analysis Plan Protocol N. BIIT0215– Platinum	Pag. 14 di 18
---	---	---------------

For the clinical laboratory data, descriptive statistics will be generated for all tests performed. Laboratory abnormalities will be determined in accordance with the normal ranges of the clinical laboratory. Laboratory abnormalities will be tabulated.

13. Tables

The following tables will be repeated for each visit, if applicable.

- P1. Number and percentage of patients enrolled per center
- P2. Number and percentage of patients stratified by gender; mean and median age, range and interquartile range;

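### The mixed model for satisfaction and patient factors has no visit term, so a clinical factor entered visit by visit can appear associated with satisfaction merely because both averages move after T0

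*SAP*

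**What the plan says.** For the secondary objective on what goes with satisfaction, SAP section 11.b and Protocol section 16.3.4 both say that "generalized linear mixed models for repeated measurements will be performed". The factors are "social-demographic factors (age, sex, employment working, level of education, etc.) and clinical characteristics (ARR, disability, etc". Only the SAP gives model terms, in the command "mixed var1 var2 || patient": one outcome, one factor and a random intercept per patient.

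The adjusted ANOVA command in the same SAP section is "anova var1 var2 time, repeated(time". It lists time separately from var2, so var2 is not shorthand for visit. SAP section 10 remarks that "the mixed model is capable of treating time as either a continuous variable or a categorical variable or both". That describes what such a model can do, within a passage on an optional additional analysis; it does not put visit into this one.

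In the Protocol's Schedule of Events (section 4.2), "Clinical and neurological evaluation (including recording of relapses and EDSS" is marked at T0, T1, T2 and early termination, while "Social-demographics (e.g., age, gender" is marked at T0 only. Neither document says whether ARR and disability enter the model as T0 or visit values.

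**The concern.** T0 satisfaction is rated on the previous interferon by patients selected for a convenience score below 58. T1 and T2 are rated on Peg-IFN. The mean should therefore rise after T0, partly through the switch and partly through regression to the mean. Without a visit term, the model explains that rise with whatever else moves between the same visits. A factor whose average falls or rises after T0 for its own reasons then picks up a non-zero coefficient, even if patients with high and low values are equally satisfied at every visit.

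At stake is the error rate of a named secondary objective. The SAP intends its results for publication and calls a result significant when p is "less or equal to a type I error =0.05 (two-sided test".

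**Working it through.** **The plan's own figure.** No figure is given for this model. The sample-size statement (SAP section 6: 250 subjects, 3 points, SD of change 16, power 90%) serves here only as a source of inputs. For the record, 3√250/16 = 2.965. Two-sided, 2.965 − 1.960 = 1.005, or 84% power. One-sided, 2.965 − 1.645 = 1.320, or 91%. So the stated 90% matches a one-sided test, although the SAP specifies two-sided. Nothing below rests on that.

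**Inputs from the documents.** 250 patients; three visits; baseline mean 55, SD 16; SD of change 16; entry cut below 58; two-sided 0.05. The two SDs imply a between-visit correlation r: 16² = 2·16²·(1 − r), so r = 0.5, that is, variance 128 between and 128 within patients.

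**Assumed inputs.** The factor's mean shift d after T0 (in SD); its within-patient correlation ρ (0.5 and 0.9); satisfaction rises other than 3 points; equal means at T1 and T2; normality; no dropout.

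**Size of the rise from selection alone.** Scores between 0 and 58 with mean 55 have an SD of at most √(3 × 55) = 12.8, so 55 (SD 16) cannot describe the enrolled patients. Take it as the unselected population. The cut lies at (58 − 55)/16 = 0.1875 SD, so the mean below it is 55 − 16 × 0.392/0.574 ≈ 44.1. With correlation 0.5, the expected rise without any treatment effect is 0.5 × 10.9 ≈ 5.5 points.

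**Spurious slope.** Let satisfaction rise by S and the factor shift by d after T0, with the two otherwise independent. With visit pattern (0, 1, 1) and variance ratio 1, the random-intercept fit gives between-patient variation weight 1/(1 + 3) = 1/4. The slope without a visit term is then about

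(2/9)dS ÷ [(2/3)(1 − ρ) + (2/9)d² + (1/4)(ρ + (1 − ρ)/3)].

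For S = 3 and d = 0.5:
- ρ = 0.5: 0.333 / (0.333 + 0.056 + 0.167) = 0.60 points per SD (simulated 0.60).
- ρ = 0.9: 0.333 / (0.067 + 0.056 + 0.233) = 0.94 (simulated 0.90).

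The numerator is zero if d = 0, or once visit is in the model.

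**False-positive rate, no entry cut** (1,000 trials per case; ranges span the two values of ρ):

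| Rise in satisfaction | d = 0 | d = 0.1 | d = 0.2 | d = 0.5 |
|---|---|---|---|---|
| 3 (plan) | 5.0–5.3% | 4.7–5.5% | 6.9–8.6% | 19.4–25.8% |
| 10 (assumed) | 5.0–7.4% | 8.3–12.9% | 25.0–36.8% | 87.9–98.4% |
| 20 (assumed) | 5.1–6.5% | 14.6–16.6% | 43.2–56.9% | 99.6–99.9% |

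With categorical visit added, every case lies between 3.9% and 7.2% (Monte Carlo SE about 0.7 points). A factor fixed within patient gives 5.0% with or without visit.

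**With the entry cut below 58** (one set of runs, 1,000 trials per case):

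| True rise added to selection | d = 0.25 | d = 0.5 |
|---|---|---|
| 0 | 15% | 45% |
| 3 | 28% | 77% |
| 6 | 37% | 91% |

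With visit, these cases give 3.5–6.3%. Other runs under different assumptions about the factor widen the ranges to roughly 15–40% at 0.25 SD and 34–94% at 0.5 SD. At about 0.1 SD the rate is roughly 6–11%.

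**One route to a shift without clinical change.** SAP section 8 takes baseline relapses over the previous 12 months, and table P15 counts episodes since the last visit, about 12 weeks. If raw counts were entered, a constant rate would still lower the mean by 1 − 12/52 = 77%. At an assumed 0.2 to 0.5 relapses per year (Poisson), that is 0.154/0.447 = 0.34 SD to 0.385/0.707 = 0.54 SD. Properly annualised at a constant rate, the shift vanishes.

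**The case against.** A reader might infer that any factor that changes after the switch is biased, or that the whole satisfaction analysis is unsound. The documents and the check do not support that. A factor that varies within patients without an average shift rejects at 5.0–7.4%, about as it does with visit in the model. Age, sex, education and, on the Schedule of Events, employment are recorded at T0 only, and with complete data they are unaffected. The exposed factors are relapse rate, disability and whatever the unspecified remainder of the list contains.

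Nor is the use of visit-level values documented. EDSS is a baseline adjuster in the ANOVA, and ARR is an endpoint at 24 weeks with no visit-level definition. If T0 values are used, there is no bias. The outcome might also be the change score, in which case T0 drops out of it. The commands are templates: one var2 stands for five adjusters in the ANOVA. These points stand as limits. They do not supply the missing term, since the ANOVA template does print time.

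The factor shifts are assumed. For disability the nearest guide is the pivotal trial in Protocol section 5.1, where 6.8% had 12-week confirmed progression at one year. Taking about 1 point each, the mean shift is about 0.07 points, or 0.05–0.07 SD if the SD is 1 to 1.5 (assumed, and in a different population). At 0.05–0.1 SD, with the entry cut, the false-positive rate was 5–9% from selection alone and 7–14% with a 6-point rise added. So for EDSS the inflation may be slight; relapse counts could move more. The larger percentages also reflect an observed rise of about 5.5 + 6 = 11.5 points, well above the plan's 3.

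Finally, the objective speaks only of a relationship. Adjusting for visit removes any genuinely shared mean change as well, so the estimand should be stated.

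**Conclusion.** The point holds in conditional form. The printed command omits visit, and nothing else in either document restores it. Followed literally with visit-level clinical factors, it can produce a significant association that is absent within visits. The condition is that the factor's average moves between visits along with satisfaction.

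The size runs from negligible (shifts near 0.1 SD or less with a small rise) to severe (0.5 SD with the entry cut and a true rise). No particular error rate can be attributed to this trial, because neither document states the factor shift or which value enters. The results rest on a between-visit correlation of 0.5, normal scores, independence of factor and satisfaction within each visit, and complete data.

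The change is worth making before analysis, but its weight is modest: this is a secondary association, none of tables P1 to P41 reports it, and the primary endpoint is not involved.

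**What to change.** Change the command in SAP section 11.b to `mixed var1 var2 i.visit || patient:`. For each clinical factor, state whether the T0 or the visit value is used. If relapses enter by visit, say how they are annualised, and say whether var1 is the score or its change from baseline. Add one sentence saying that the coefficient describes the association within visits.

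The cost is two degrees of freedom and a few lines of text; no new data are needed. A factor-by-visit interaction, or a separate display for T1 and T2, is optional: the visit main effect alone brought the error rate back to about 5%.

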#### **15.1.2. Adverse Event**

An AE is any untoward medical occurrence in a patient or clinical investigation subject administered a pharmaceutical product and that does not necessarily have a causal relationship with this treatment. An AE can therefore be any unfavorable and unintended sign (including an abnormal laboratory finding), symptom, or disease temporally associated with the use of a medicinal (investigational) product, whether or not related to the medicinal (investigational) product.

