### 15.3.2. Severity of Events

The following definitions should be considered when evaluating the severity of AEs and SAEs:

Severity of Event	
Mild	Symptom(s) barely noticeable to subject or does not make subject uncomfortable; does not influence performance or functioning; prescription drug not ordinarily needed for relief of symptom(s) but may be given because of personality of subject.
Moderate	Symptom(s) of a sufficient severity to make subject uncomfortable; performance of daily activity is influenced; subject is able to continue in study; treatment for symptom(s) may be needed.
Severe	Symptom(s) cause severe discomfort; symptoms cause incapacitation or significant impact on subject’s daily life; severity may cause cessation of treatment with study treatment; treatment for symptom(s) may be given and/or subject hospitalized.

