### 15.3.3. Expectedness of Events

Like all medicines, Peg-IFN (Plegridy®) can cause side effects, although not everybody gets them. In accordance with the clinical experience of the marketed product, the following events may occur to Peg-IFN (Plegridy®) users:

Serious side effects

- Liver problems
- Depression
- Serious allergic reaction
- Seizures
- Injection site damage
- Kidney problems including scarring that may reduce your kidney function

- Blood problems

- Other side effects (very common side effects, flu-like symptoms, nausea or vomiting, pruritus, hives).

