P21. Number and percentage of patient who have correctly taken the prescribed doses of treatment within the last 28 days; if don't, mean and median, interquartile range and range of injections have not been performed during the last 28 days;

P22. Number and percentage of patients per reasons to non correctly taken the treatment:

- a) Anxiety for injection
- b) Skin reaction
- c) Forgot to take the dose
- d) Pain at the injection site

- e) Depression
- f) Headhache
- g) Fatigue
- h) Flu-like symptoms
- i) “I did not want to”
- j) “I am not sure of the benefits”
- k) “I am tired of injections”
- l) No one available for injection
- m) Uncomfortable dosing
- n) “I am pregnant / I have planned a pregnancy”
- o) Other

- P23. Mean and median, interquartile range and range of injections expected from the therapy taken in the last 28 days;
- P24. Mean and median, interquartile range and range of MSTCQ;
- P25. Change from baseline in the score of the MSTCQ at 12 and 24 weeks;
- P26. Adjusted repeated measures analysis of variance for change of the MSTCQ at 12 and 24 weeks;
- P27. Mean and median, interquartile range and range of MusiQol;
- P28. Change from baseline in the score of the MusiQol at 12 and 24 weeks;
- P29. Adjusted repeated measures analysis of variance for change of the MusiQol at 12 and 24 weeks;
- P30. Mean and median, interquartile range and range of FSS;
- P31. Change from baseline in the score of the FSS at 12 and 24 weeks;
- P32. Adjusted repeated measures analysis of variance for change of the FSS at 12 and 24 weeks;
- P33. Mean and median, interquartile range and range of EDSS;
- P34. Change from baseline in the score of the EDSS at 12 and 24 weeks;
- P35. ARR, Annualized Relapse Rate
- P36. Number and percentage of abnormalities in laboratory values per each test;
- P37. List of all laboratory abnormalities;
- P38. Number and percentage of adverse events stratified by severity;

	
Statistical Analysis Plan Protocol N. BIIT0215– Platinum
	
Pag. 18 di 18

--	---	---

- P39. List of all adverse events with related characteristics;
- P40. Number and percentage of patients who discontinued the study and reasons of discontinuity;
- P41. Number and percentage of patients who experienced pregnancy during the study and outcome of pregnancy.

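### The laboratory abnormality count carries neither size nor direction and adverse-event severity has no laboratory criterion, so the number of patients with a marked liver, kidney or blood abnormality cannot be read from the planned tables

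*SAP*

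**What the plan says.** **Laboratory data.** SAP 12.b, matching protocol 16.4.2, first promises summaries: "For the clinical laboratory data, descriptive statistics will be generated for all tests performed". The protocol synopsis gives their form for all collected variables: mean, SD, median and range at T0, T1 and T2, and changes from baseline. SAP 12.b then defines abnormality: "Laboratory abnormalities will be determined in accordance with the normal ranges of the clinical laboratory. Laboratory abnormalities will be tabulated". In SAP 13, P36 is "Number and percentage of abnormalities in laboratory values per each test" and P37 lists all abnormalities. Tables are repeated by visit where applicable. The table list has a descriptive table for vital signs (P14) but none for laboratory values.

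**Tests.** Protocol 14.2 and SAP 8 name 13 haematology and 6 chemistry tests, to be done at the investigator's discretion. The schedule in protocol 4.2 marks routine laboratory tests at every visit.

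**Adverse events.** Protocol 15.1.2 includes "any unfavorable and unintended sign (including an abnormal laboratory finding), symptom, or disease". Protocol 15.3.2 defines Mild first as "Symptom(s) barely noticeable to subject or does not make subject uncomfortable; does not influence performance or functioning". Moderate and Severe are also worded around symptoms and daily life. P38 reports "Number and percentage of adverse events stratified by severity".

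**Known risks and endpoints.** Protocol 15.3.3 lists liver problems, blood problems and "Kidney problems including scarring that may reduce your kidney function" among serious side effects. Protocol 6.2.2 makes both adverse-event severity and laboratory abnormalities secondary endpoints.

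**The concern.** The tests chosen cover the organs that the protocol names as at risk, but the count that summarises them does not separate a value just outside the range from one many times the limit. Nor does the SAP say whether a value in the harmless direction is counted apart from one in the harmful direction.

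The severity table does not clearly fill the gap. A symptom-free enzyme rise or low blood count that is reported as an adverse event meets a scale with nothing to say about laboratory size, so its grade is left to each investigator across 35 planned sites.

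What is at stake is how two secondary safety endpoints can be read. The overall abnormality rate may consist largely of trivial values, while the number of patients with a relevant organ abnormality after the switch is not tabulated. Protocol 5.1 states that no data exist from patients switching between non-pegylated and pegylated interferon, which is this study's population.

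**Working it through.** The plan gives no figure of its own to reproduce here. The check asks which planned output separates a marked from a trivial abnormality, and then how many flags chance alone would produce.

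**1. What each output can show**

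- P36: yes or no against the range, counted per test. No size, and no stated direction. Its unit is abnormalities, not patients, and no denominator is given.
- Descriptive statistics: centre, spread and extremes. The maximum shows that an extreme value occurred, not how many patients had one.
- P37: every abnormality is listed, but the SAP does not say that the value or the normal range is printed.
- Adverse events by type (SAP 12.a): counts laboratory findings that were reported as events, without size.
- P38: investigator severity, on a scale without a laboratory criterion.

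**2. Illustration (assumed values)**

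Take 250 patients, 249 at 0.5 times the upper limit of normal (ULN) and one abnormal at x times ULN.

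- P36 count = 1/250 = 0.4% for any x above 1.
- Mean = (249 × 0.5 + x)/250 = (124.5 + x)/250.
- Maximum = x.

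| x (times ULN) | P36 | Mean (times ULN) | Maximum (times ULN) |
|---|---|---|---|
| 1.1 | 1/250 | 0.502 | 1.1 |
| 3 | 1/250 | 0.510 | 3 |
| 5 | 1/250 | 0.518 | 5 |
| 10 | 1/250 | 0.538 | 10 |

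The count does not change and the mean hardly moves. Only the maximum responds, and it would read the same if several patients reached it.

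**3. Background of chance flags (upper figures)**

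Assumptions, none stated in the documents: normal ranges are two-sided 95% reference intervals, all 275 patients have all 19 tests at all 3 visits, and there is no drug or disease effect.

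- Results: 275 × 19 × 3 = 15,675.
- Flags expected: 15,675 × 0.05 = 784. One third (about 261) fall at T0, before treatment.
- At least one flag at a visit, if tests were independent: 1 − 0.95^19 = 0.62.
- ALT at one visit: 275 × 0.05 = 13.75 flags (binomial 95% range 7 to 21), of which 275 × 0.025 = 6.9 are low.
- If a fraction p has a true marked ALT rise, expected flags = 275 × [p + (1 − p) × 0.05]. For p = 0.5%, 1% and 2% this gives 15.1, 16.4 and 19.0, all inside 7 to 21.

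Under these assumptions, a few marked rises would not stand out in the P36 row.

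**The case against.** The strongest reply is that the plan does more with laboratory data than P36 alone suggests, and three stronger readings fail on the documents.

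- *A reader might infer that laboratory results are summarised only as inside or outside the range.* They are not. Descriptive statistics with ranges are planned for every test, P37 lists every abnormality, and P36 can be compared with its own T0 version.
- *A reader might infer that a symptom-free abnormality is graded mild by rule.* No text says so. The definitions are for the investigator to consider, and Severe also mentions stopping treatment and hospitalisation. Mild is a likely reading where the scale is silent.
- *A reader might infer that marked organ harm escapes the reporting altogether.* Seriousness is judged separately from severity. Protocol 15.1.3 allows medically important events to be serious, and Appendix G names hepatitis, renal failure, pancytopenia and aplastic anemia. Adverse events are also tabulated by type, and discontinuations by reason (P40).

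The chance-flag arithmetic is also open to challenge. Testing is discretionary, so the totals are maxima. Red-cell measures overlap, so 62% is too high. No hypothesis test on P36 is planned. Finally, this is an on-label Phase IV study of patient-reported outcomes, and its primary result does not depend on laboratory tables.

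All of this stands, and it limits the point without removing it. Ranges and listings do not give a number of patients, Appendix G names diagnoses rather than laboratory thresholds, and adverse-event type carries no size.

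**Conclusion.** The point holds in a limited form. P36 is a yes/no count without size or direction, and protocol 15.3.2 has no laboratory criterion. No planned table therefore gives the number of patients with a marked liver, kidney or blood abnormality, although laboratory abnormalities are a secondary endpoint and these organ risks are named in the protocol. A reader would have to derive that number from P37, which may not show the values.

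The gap in P36 follows from the text and needs no assumption. The size of the background noise does: 15,675 results, 784 flags and 62% are upper figures under assumed 95% reference intervals and full testing, with independence also needed for the 62%. The conclusion does not rest on them. This is a worthwhile and cheap improvement in safety reporting. It does not affect the primary analysis and implies no rule for treatment.

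**What to change.** Change the reporting in the SAP only.

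1. **SAP 12.b and P36:** for the liver, kidney and blood-count tests, add the number and percentage of patients by worst post-baseline value in the harmful direction, next to their baseline category. Use one pre-specified, test-specific laboratory grading scale, or multiples of the laboratory's own limit. Liver enzymes and creatinine should not share a single set of cut-offs. Because testing is discretionary, use patients tested as the denominator and state it.
2. **P37:** print the value and the normal range with each abnormality.
3. **P38:** keep the investigator's severity as recorded. For adverse events that are laboratory findings, show the laboratory grade beside it.

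The cost is SAP wording and one or two more tables. Applying 12.b already requires each value and its normal range, but the documents do not say that the numerical limits are stored, so confirm that they are. The downside is that some events will look more severe by laboratory grade than by the symptom scale. Showing both makes that difference visible without overriding the investigator.
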